8.1.3.4.4 Congenital Anomalies/Birth Defects

Any congenital anomaly/birth defect in a child born to a female patient exposed to the medicine should be classified as an SAE, recorded in the AE section of the eCRF, and reported to the MAH immediately (i.e., no more than 24 hours after learning of the event; see [Section 8.1.3.1](#)).

8.1.4 Follow-Up of Patients after Adverse Events

8.1.4.1 HCP Follow-Up

The HCP should follow each AE until the event has resolved to baseline grade or the event is assessed as stable by the HCP, the patient is lost to follow-up, or the patient withdraws consent. Every effort should be made to follow all SAEs considered to be related to the studied medicinal product until a final outcome can be reported.

During the study period, resolution of AEs (with dates) should be documented in the AE section of the eCRF and in the patient's medical record to facilitate SDV.

All pregnancies reported during the study should be followed by the treating physician until pregnancy outcome.

8.1.4.2 Marketing Authorization Holder Follow-Up

For all AEs, the MAH or a designee may follow-up by telephone, fax, electronic mail, and/or a monitoring visit to obtain additional case details and outcome information (e.g., from hospital discharge summaries, consultant reports, autopsy reports) in order to perform an independent medical assessment of the reported case. AE follow-up should be documented in the AE section of the eCRF.

8.2 SAFETY REPORTING REQUIREMENTS FOR NON-STUDIED PRODUCTS

Although AE information is not being actively solicited for non-studied products, the treating physician/consumers are reminded to report any adverse reactions (for which they suspect a causal role of a product) that come to their attention to the MAH of the suspected product, or to the concerned competent authorities via the national spontaneous reporting system.

In addition, the following should also be reported if occurring during exposure to a marketed medicinal product, even in the absence of AEs:

- Pregnancy
- Breastfeeding

- Abnormal laboratory findings
- Overdose, abuse, misuse, off-label use, medication error, or occupational exposure
- Reports of lack of efficacy
- Product quality defects and falsified medicinal products
- Data related to a suspected transmission of an infectious agent via a medicinal product
- Drug interactions (including drug/drug, drug/food, drug/device, and drug/alcohol)

When a patient is not exposed to a marketed medicinal product, but the HCP/consumer becomes aware of the potential for a medication error, or an intercepted medication error, this should also be reported.

8.3 REPORTING OF PRODUCT COMPLAINTS WITHOUT ADVERSE EVENTS

Report Roche product complaints without AEs, where Product Complaint is any written or oral information received from a complainant that alleges deficiencies related to identity, quality, safety, strength, purity, reliability, durability, effectiveness, or performance of a product after it has been released and distributed to the commercial market, to [contact]. Report non-Roche-product complaints as per local regulation.

9 PUBLICATION OF DATA AND PROTECTION OF TRADE SECRETS

Regardless of the outcome of a study, Roche is dedicated to openly providing information on the study to healthcare professionals and to the public, both at scientific congresses and in peer-reviewed journals. Roche will comply with all requirements for publication of study results.

The results of this study may be published or presented at scientific meetings. If this is foreseen, the treating physician must agree to submit all manuscripts or abstracts to the MAH prior to submission for publication or presentation. This allows Roche to protect proprietary information and to provide comments based on information from other studies that may not yet be available to the treating physician.

In accordance with standard editorial and ethical practice, Roche will generally support publication of multicenter studies only in their entirety or by region and not as individual center data. In this case, a coordinating physician will be designated by mutual agreement.

Authorship will be determined by mutual agreement and in line with International Committee of Medical Journal Editors' authorship requirements. Any formal publication of the study in which contribution of Roche personnel exceeded that of conventional monitoring will be considered as a joint publication by the physician and the appropriate Roche personnel.

Any inventions and resulting patents, improvements, and/or know-how originating from the use of data from this study will become and remain the exclusive and unburdened property of the MAH, except were agreed otherwise.

Specification of Publication Plan

The publication plan for this study will be prepared as a separate document.

11 APPENDICES

Appendix 1 List of Stand-Alone Documents Not Included in the Protocol

Country appendix, if applicable

Appendix 2 Data Collection Overview (as per Standard of Care)

Data Collection Schedule for FaReal Study

Data Collection ¹	Retrospective Data Collection	Data Collection at Enrollment Visit ⁷ / Baseline/Index Visit ⁸	Data Collected During Prospective Observational Period ⁹	
			Month 3, 6, 12 and 24 visits	Any other routine visits
Informed consent (as required per local regulations)		x		
Eligibility ²		x		
Demographic characteristics (year of birth, sex, smoking status)		x		
Disease information (including type of disease and date of diagnosis, disease characteristics) ³		x	x	x
Medical and surgical history (ocular, by eye where applicable) ³		x		
Prior treatment and management, by eye (treatment details, details of other procedures) ³	x			
Treatment and management (by eye) during study period (treatment details, treatment regimen/management plan including monitoring and injection visit intervals, planned and actual visit dates and reasons for delays if applicable, treatment switch and treatment discontinuation/termination) ³		x	x	x
Concomitant medications (ocular)		x	x	x

VA (Method of VA Assessment - Scale and Type of Correction and other assessments) ⁴		x	x	x
Imaging assessments (type, machine used, and the results) by eye, as per routine clinical practice (during visits for the retinal indications) ⁵		x	x	x
Safety events (all ocular and non-ocular AEs) ⁶		x	x	x

AE = adverse event, SAE = serious adverse event, VA = visual acuity.

1. Variables obtained according to routine clinical practice. No additional diagnostic or monitoring procedures shall be applied to the patients.
2. Signed informed consent must be obtained before any data collection.
3. Images taken as per routine clinical practice for the specified indications of interest will not be collected for this study.
4. The following will be collected from index date (i.e., date of treatment initiation with faricimab) until the end of the observational period: SAEs and non-serious AEs (including severity of all AEs and AEs of special interest).
5. Enrollment is the date the patient signs the Informed Consent Form to participate in this study.
6. Baseline is the date when a patient initiates treatment with faricimab in at least one eye. Index date is the date when treatment is initiated at the eye-level. If both eyes are treated with faricimab and the treatment start dates are different, each start date will be used as index date for the respective eye.
7. The prospective observational period starts one day post-enrollment.
8. Baseline is the date when a patient initiates treatment with faricimab in at least one eye. Index date is the date when treatment is initiated at the eye-level. If both eyes are treated with faricimab and the treatment start dates are different, each start date will be used as index date for the respective eye.
9. The prospective observational period starts one day post-enrollment.

Appendix 3 **Error! Reference source not found.** Conversion Table for Visual Acuity

Snellen acuity and Logarithm of the Minimum Angle of Resolution (LogMAR) acuity score will be converted to approximate Early Treatment Diabetic Retinopathy Study (ETDRS) letter score (Gregori et al.,2010; Holladay, 1997). The general formulas are:

- Approximate ETDRS (letter score) = 85 + 50 × log (Snellen fraction); or:
- Approximate ETDRS (letter score) = 85 – 50 × LogMAR.

Table 1. Conversion of Visual Acuity Measurements Between Snellen Fraction, logMAR, ETDRS Letter Scores, ETDRS Equivalent Snellen Fraction, and Approximate ETDRS Letter Scores

Snellen Fraction	ETDRS Equivalent Snellen Fraction	logMAR*	ETDRS Letter Score	Approximate ETDRS Letter Score†
1/200 (CF)		2.30		0
2/200		2.00		2
	20/800	1.60	5	5
6/200		1.52		9
	20/640	1.51	10	10
	20/500	1.40	15	15
20/400	20/400	1.30	20	20
	20/320	1.20	25	25
20/300		1.18		26
	20/252	1.10	30	30
20/250		1.10		30
20/200	20/200	1.00	35	35
	20/160	0.90	40	40
	20/125	0.80	45	45
20/100	20/100	0.70	50	50
20/80	20/80	0.60	55	55
20/70		0.54		58
	20/63	0.50	60	60
20/60		0.48		61
20/50	20/50	0.40	65	65
20/40	20/40	0.30	70	70
	20/32	0.20	75	75
20/30		0.18		76
	20/25	0.10	80	80
20/20	20/20	0.00	85	85
	20/16	-0.10	90	90
20/15		-0.12		91
	20/13	-0.19	95	95
	20/10	-0.30	100	100

*Snellen converted to logMAR = -1 × log(Snellen fraction).
 †Snellen converted to approximate ETDRS letters = 85 + 50 × log(Snellen fraction), which may be rounded to the nearest letter.
 CF, counting fingers.

Holladay TJ. Proper Method for calculating Average Visual Acuity. Journal of Refractive Surgery 1997;13:388-91.

The following approximate conversion will be used for off-chart values ([Mollan et al., 2021](#)):

Off-chart Categories	Snellen feet	Snellen meter	Snellen decimal	LogMAR	ETDRS
NLP	20/20000	6/6000	0.001	3	0
LP	20/10000	6/3000	0.002	2.7	0
HM	20/4000	6/1200	0.005	2.3	0
CF	20/2000	6/600	0.01	1.9	2

Abbreviations:

CF= counting fingers, ETDRS= Early Treatment Diabetic Retinopathy Study, HM= hand movement, LogMAR= Logarithm of the Minimum Angle of Resolution, LP= light perception, NLP= no light perception.

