 - Details of other procedures that could potentially elevate/deteriorate VA.
- Imaging assessments (by eye) during the study period from index date until end of study participation, include but not limited to:
 - optical coherence tomography (OCT)-imaging assessment type, machine used, and the results of CST, IRF, SRF, PED. Images will not be collected.

The primary effectiveness variable is VA. VA will be collected as measured per local practice and will then be entered from source data into electronic case report form (eCRF) using the approximate Early Treatment Diabetic Retinopathy Study (ETDRS) letter score.

Data Sources

Patients' data will be recorded on eCRFs and stored in the electronic data capture (EDC) system. All clinical data will be processed and stored in a database. All data will be pseudo-anonymized, and each patient will have a unique code so that the information of the same patients can be linked.

Faricimab—F. Hoffmann-La Roche Ltd
Protocol MR45586, Version 1.0

Data Analysis

Full details of the statistical analysis to be conducted will be provided in the SAP.

The following 2 cohorts will be defined and analyzed:

- Cohort 1: Patients receiving faricimab for nAMD in at least one eye
- Cohort 2: Patients receiving faricimab for DME in at least one eye.

Within each cohort, sub-cohorts will be defined as per treatment history at eye-level when initiating faricimab for this study as described below.

The following sub-cohorts will be considered:

- A. Treatment naïve sub-cohort:
Patient-eyes initiating faricimab intravitreal treatment that have never had any anti-VEGF intravitreal treatment
- B. Previously treated with anti-VEGF sub-cohort
Patient-eyes initiating faricimab intravitreal treatment after being previously treated with any intravitreal anti-VEGF.

Sub-cohort Details per Cohort

Cohort 1	Cohort 2
Patients receiving faricimab for nAMD in at least one eye	Patients receiving faricimab for DME in at least one eye
A. Treatment naïve sub-cohort: Patient-eyes newly initiating faricimab intravitreal treatment* in at least one eye that has never had any anti-VEGF intravitreal treatment	A. Treatment naïve sub-cohort: Patient-eyes newly initiating faricimab intravitreal treatment* in at least one eye that has never had any anti-VEGF intravitreal treatment

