6.3.1 Visual Acuity

The primary effectiveness variable is VA. VA will be collected at index date and at all available follow-up measurements. Information on the scale and type of correction (e.g., Best-corrected, Corrected, Pinhole, Uncorrected) during assessment, and the date of assessment, will be collected for each VA assessment, as available per routine clinical practice. If possible, and within routine clinical practice, it is recommended that the patient is assessed in the same manner across visits.

VA will be collected as measured per local practice and will then be converted automatically in the eCRF to the approximate ETDRS letter score ([Gregori et al., 2010](#)). Details of the conversion to approximate ETDRS letter score are outlined in [Appendix 3](#).

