6.7.2 Effectiveness Analyses

6.7.2.1 Primary Effectiveness Analyses

Primary effectiveness analyses will be performed per cohort and per sub-cohort, at the eye-level, for the EFAS-EL.

The primary effectiveness endpoint is the change in VA (approximate ETDRS letter score) from index date to month 12 per nAMD and DME and per treatment naïve and pre-treated sub-cohorts. VA will be measured as per the local practice at index date and at month 12. To allow statistical analysis of the different clinical methods used to measure VA, the assessments will be automatically converted to the approximate ETDRS letter score. The approximate ETDRS letter score conversion table can be found in [Appendix 3](#).

Both actual values at index date and month 12 and change from index date in VA (approximate ETDRS letter score) to month 12 will be summarized descriptively.

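### Appendix 3 does not fix one letter score for vision below 20/800, so a worsening eye can be recorded as a gain on the primary endpoint

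*Protocol*

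**What the plan says.** Protocol section 6.7.2.1 defines the endpoint: "The primary effectiveness endpoint is the change in VA (approximate ETDRS letter score) from index date to month 12 per nAMD and DME". It refers to Appendix 3 for the conversion, as does section 6.3.1.

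Appendix 3 contains three rules:

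- **General formulas.** "Approximate ETDRS (letter score) = 85 + 50 × log (Snellen fraction); or", with the logMAR equivalent "Approximate ETDRS (letter score) = 85 – 50 × LogMAR". Neither states a lower limit.
- **Table 1 of the appendix.** Its footnote derives the Snellen scores from the same formula, "which may be rounded to the nearest letter". The two lowest rows are 2/200 (logMAR 2.00, score 2) and 1/200, labelled counting fingers (logMAR 2.30, score 0).
- **Off-chart table.** "The following approximate conversion will be used for off-chart values". The counting-fingers row reads "CF 20/2000 6/600 0.01 1.9 2". Hand movement (20/4000, logMAR 2.3), light perception (logMAR 2.7) and no light perception (logMAR 3) all score 0.

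The appendix does not say which rule prevails where they differ.

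On data entry, the synopsis says that VA "will then be entered from source data into electronic case report form (eCRF) using the approximate" letter score. Section 6.3.1 says that it is "converted automatically in the eCRF to the approximate ETDRS letter score", and sections 6.1.2 and 6.7.2.1 agree with that.

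**The concern.** A programmer building the automatic conversion cannot implement Appendix 3 as written for very low vision without choosing between contradictory values. The choice matters because this score is the primary endpoint and also defines the gain and loss categories in section 6.7.4.

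The awkward case is also a natural one. An eye that declines beyond the chart moves from a numeric value, scored by formula, to an off-chart category, scored by table. If the formula gives a negative number and the table gives 0 or 2, the decline appears as an improvement. Such eyes stay in the analysis: the entry criteria in section 6.2 set no acuity limit, and section 6.7.4.4 names eyes with off-chart values as a possible subgroup.

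**Working it through.** **1. Reproducing Table 1 of Appendix 3.** Inputs are the printed Snellen fraction and logMAR of each of the 29 rows, put through 85 + 50 × log10(fraction) and 85 − 50 × logMAR. The 27 rows at 20/800 and better reproduce within 1 letter (for example 20/800: 85 − 50 × 1.60 = 5, printed 5). The two lowest do not:

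| Row | Formula | Printed |
|---|---|---|
| 2/200, logMAR 2.00 | 85 − 100 = −15 | 2 |
| 1/200, logMAR 2.30 | 85 − 115 = −30 | 0 |

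**2. The off-chart table against the formula**, using the printed logMAR:

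| Category | Formula | Printed |
|---|---|---|
| Counting fingers, 1.9 | 85 − 95 = −10 | 2 |
| Hand movement, 2.3 | 85 − 115 = −30 | 0 |
| Light perception, 2.7 | 85 − 135 = −50 | 0 |
| No light perception, 3 | 85 − 150 = −65 | 0 |

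The counting-fingers row is also inconsistent within itself. 20/2000 is decimal 0.01, and −log10(0.01) = 2.00, not 1.9. Table 1 prints 2.00 for the same fraction, written as 2/200.

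**3. Would an unstated floor at 0 explain the tables?** Only in part. It reproduces every printed 0, but not the two printed 2s (2/200 and off-chart counting fingers), where the floored formula gives 0.

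**4. The two tables against each other.** Matched by fraction they agree: 2/200 = 20/2000 scores 2 in both, and 1/200 = 20/4000 scores 0 in both. They disagree on the label. Counting fingers is 1/200 (score 0) in Table 1 and 20/2000 (score 2) in the off-chart table, and logMAR 2.3 is counting fingers in one and hand movement in the other. That conflict is worth 2 letters.

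**5. Worsening recorded as a gain.** Table 1 has no row between logMAR 1.60 and 2.00, so the formula is the only rule there. It falls below 2, the counting-fingers score, once logMAR exceeds 1.66 (85 − 50 × 1.66 = 2).

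- Numeric logMAR 1.8 to counting fingers: 2 − (85 − 90) = 2 − (−5) = +7. With the formula floored at 0: 2 − 0 = +2.
- Numeric logMAR 2.0, scored by formula, to no light perception: 0 − (−15) = +15, which meets the highest gain category in section 6.7.4.

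**6. Effect on a sub-cohort mean.** Shift = share of eyes affected × discrepancy. The protocol gives no share; 1–5%, all shifted in one direction, is an assumption.

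- 2-letter conflict: 0.01 × 2 = 0.02 to 0.05 × 2 = 0.10 letters.
- 30-letter gap (logMAR 2.3 typed as a number): 0.01 × 30 = 0.3 to 0.05 × 30 = 1.5 letters.

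For scale, Table 3 in section 6.7.6 gives full confidence-interval widths of 2.5 to 5.6 letters, so half-widths of 1.25 to 2.8. Those widths reproduce to rounding as 2 × 1.96 × SD / √(0.95 × n); for n = 240 this gives 3.12 at SD 12 and 3.63 at SD 14, against the stated 3 and 3.6.

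**The case against.** The off-chart table has its own instruction, so an eye entered as a category is scored from that table and never meets the formula. A reader might infer from step 2 that every hand-movement or no-light-perception eye is open to a 30- to 65-letter discrepancy. The protocol does not support that: such gaps need a numeric logMAR or Snellen value scored by the unfloored formula.

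Nor is either table out of order. Table 1 runs 5, 2, 0 as vision falls from 20/800, and the off-chart table runs 2, 0, 0, 0. Used throughout, the formula also ranks correctly: logMAR 1.8 to 2.0 is −5 to −15, a loss. A false gain needs formula and table to be mixed within one eye. Section 6.3.1 recommends assessing the patient in the same way across visits, and section 6.9 expects a consistent method. With a floor, the artefact is 2 letters, which touches only the category of any gain above zero.

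These limits stand. They do not remove the defect: formula and table can mix in an eye that falls off the chart even when the site's method is consistent, because the category replaces the number when the chart can no longer be read.

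A reader might also infer from the synopsis sentence that the original measurement is lost if sites convert by hand. That is poorly supported. The same synopsis paragraph has VA collected as locally measured, section 6.1.2 says it is documented that way, section 6.3.1 also collects scale and correction type, and section 6.6.3 requires source documents to be retained. The synopsis wording is loose and needs aligning.

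**Conclusion.** The inconsistency is real and lies in the protocol's own definition of its primary variable. Below 20/800 the appendix does not yield one score per acuity, and worsening can be recorded as a gain of 7 letters (2 if floored), or 15 in the case shown. Those per-eye results follow from the printed rules alone, provided a numeric entry is scored by the formula.

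The effect on the mean is probably small: 0.02–0.10 letters for the counting-fingers conflict at an assumed 1–5% of eyes shifted in one direction. A figure near 1.5 letters would need 5% of eyes, all mis-scored by 30 letters, all the same way. That is an extreme case and should not be read as an expected bias. The study is descriptive, without hypothesis testing, and only very low vision is affected. The point should be fixed, but it does not put the main result in doubt.

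**What to change.** - **One rule for every entry route:** score = max(0, round(85 − 50 × logMAR)), with Snellen values first converted to logMAR, and a statement that this rule takes precedence over the tables.
- **One fixed score per off-chart category** (counting fingers, hand movement, light perception, no light perception), never above the score of a better acuity. Under the floored formula this is 0 for all four.
- **Correct the rows to match:** 2/200 and off-chart counting fingers (both now 2) become 0. The counting-fingers label and its logMAR (1.9, 2.00 or 2.30) are reconciled between the 1/200 row and the off-chart table.
- **Align the synopsis** with sections 6.1.2, 6.3.1 and 6.7.2.1: the site enters the value as measured, its scale and any off-chart category, and the eCRF converts.

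A sensitivity analysis that drops eyes off-chart at month 12 is not advisable, because it conditions on the outcome and removes the worst results. If one is wanted, restrict it to eyes off-chart at index, which section 6.7.4.4 already allows for as a subgroup.

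The cost is protocol wording, the corrected rows and a check of the eCRF derivation. No new data are needed.

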Appendix 4 Methods for Assessing and Recording Adverse Events

- 4.1 Assessment of Severity of Adverse Events
- 4.2 Assessment of Causality of Adverse Events
- 4.3 Procedures for Recording Adverse Events

Appendix 4.1 Assessment of Severity of Adverse Events

The table below provides guidance for assessing adverse event (AE) severity.

Adverse Event Severity Grading Scale

Severity	Description
Mild	Discomfort noticed, but no disruption of normal daily activity
Moderate	Discomfort sufficient to reduce or affect normal daily activity
Severe	Incapacitating with inability to work or to perform normal daily activity

Note: Regardless of severity, some events may also meet seriousness criteria. Refer to definition of a serious adverse event (SAE) (see [Section 8.1.1.2](#)).

Appendix 4.2 Assessment of Causality of Adverse Events

Physicians should use their knowledge of the patient, the circumstances surrounding the event, and an evaluation of any potential alternative causes to determine whether or not an AE is considered to be related to the study medicine, indicating “yes” or “no” accordingly. Refer to [Appendix 4.3.15](#) ISO AE categorization guidelines for the classification of AEs.

The following guidance should be taken into consideration:

- Temporal relationship of event onset to the initiation of study medicine
- Course of the event, considering especially the effects of dose reduction, discontinuation of study medicine, or reintroduction of study medicine (when applicable)
- Known association of the event with the study medicine or with similar treatments
- Known association of the event with the disease under study
- Presence of risk factors in the patient or use of concomitant medications known to increase the occurrence of the event
- Presence of non–treatment-related factors that are known to be associated with the occurrence of the event

